DATE: 23 October 2003

RE: LETTER OF AMENDMENT FOR: HPTN 049, Version 2.0, dated 11 January 2003.

Phase I Safety and Acceptability Study of the Vaginal Microbicide 6% Cellulose Sulfate Gel Among HIV-Infected Women

TO: _____, Principal Investigator, HPTU PTN XX-XXX

FROM: [name], CORE Protocol Specialist

THE FOLLOWING INFORMATION IMPACTS THE HPTN 049 STUDY (COHORT 4 ONLY) AND MUST BE FORWARDED TO YOUR INSTITUTIONAL REVIEW BOARD (IRB)/ETHICS COMMITTEE (EC) AS SOON AS POSSIBLE FOR THEIR INFORMATION AND REVIEW. THIS MUST BE APPROVED BY YOUR IRB/EC BEFORE IMPLEMENTATION.

THE FOLLOWING INFORMATION MAY ALSO IMPACT THE SAMPLE INFORMED CONSENT. YOUR IRB/EC WILL BE RESPONSIBLE FOR DETERMINING THE PROCESS OF INFORMING SUBJECTS OF THE CONTENTS OF THIS LETTER OF AMENDMENT.

PLEASE FILE THIS LETTER AND ANY IRB/EC CORRESPONDENCE IN YOUR REGULATORY FILE AND OTHER PERTINENT FILES. YOU ARE NOT REQUIRED TO SUBMIT THESE DOCUMENTS TO THE PROTOCOL REGISTRATION OFFICE UNLESS THE CHANGES RESULT IN A CHANGE TO THE INFORMED CONSENT FOR YOUR SITE.

Summary of Revisions

- For Cohort 4 only The entry criteria have been revised to include women who have had a sexually transmitted disease in the six months prior to enrollment.
- For Cohort 4 only The entry criteria have been revised to include male partners who have had a sexually transmitted disease in the six months prior to enrollment.

The changes described herein will be incorporated in the next version of Protocol HPTN 049 if it undergoes full protocol amendment at a later time.

Upon receipt of IRB approval, the following protocol modifications, indicated by strikethrough and **bold** text, will be implemented:

- 1. In the protocol Section 3.2.1, eighth bullet:
- In the six months prior to Enrollment (including at the study Screening Visit), diagnosed with or treated for any STD or pelvic inflammatory disease.

Note: Women with a history of herpes simplex virus 1 or 2 who have been asymptomatic for at least six months will not be excluded.

Note: Women with a history of genital warts in the last six months that have resolved prior to enrollment will not be excluded unless the warts were surgically removed in the three months prior to Enrollment.

- 2. In the protocol Section 3.2.1, after the fourteenth bullet:
- At enrollment is being treated for any STD.
- 3. In the protocol Section 3.2.2, at the second bullet
- In the six months prior to Enrollment, diagnosed with or treated for any STD.
- At enrollment is being treated for any STD.

DATE: 01 August 2003

RE: LETTER OF AMENDMENT FOR: HPTN 049, Version 2.0, dated 11 January 2003.

Phase I Safety and Acceptability Study of the Vaginal Microbicide 6% Cellulose Sulfate Gel Among HIV-Infected Women

- TO: ______, Principal Investigator, HPTU PTN XX-XXX
- FROM: [name], CORE Protocol Specialist

THE FOLLOWING INFORMATION IMPACTS THE HPTN 049 STUDY AND MUST BE FORWARDED TO YOUR INSTITUTIONAL REVIEW BOARD (IRB)/ETHICS COMMITTEE (EC) AS SOON AS POSSIBLE FOR THEIR INFORMATION AND REVIEW. THIS MUST BE APPROVED BY YOUR IRB/EC BEFORE IMPLEMENTATION.

THE FOLLOWING INFORMATION MAY ALSO IMPACT THE SAMPLE INFORMED CONSENT. YOUR IRB/EC WILL BE RESPONSIBLE FOR DETERMINING THE PROCESS OF INFORMING SUBJECTS OF THE CONTENTS OF THIS LETTER OF AMENDMENT.

PLEASE FILE THIS LETTER AND ANY IRB/EC CORRESPONDENCE IN YOUR REGULATORY FILE AND OTHER PERTINENT FILES. YOU ARE NOT REQUIRED TO SUBMIT THESE DOCUMENTS TO THE PROTOCOL REGISTRATION OFFICE UNLESS THE CHANGES RESULT IN A CHANGE TO THE INFORMED CONSENT FOR YOUR SITE.

Summary of Revisions

- The number of participants in Cohort 3 has been reduced from 24 to 12, and the number of participants in Cohort 4 has been reduced from 24 to 20 due to the low number of HIV infected sero-concordant couples that meet entry criteria and are interested in participating in the study.
- The study duration has been extended to 19 months.
- Other administrative clarifications have been incorporated in the protocol as needed.

Upon receipt of IRB approval, the following protocol modifications, indicated by strikethrough and **bold** text, will be implemented:

1. In the protocol Schema:

Treatment Regimen: Female participants will apply 3.5 mL of either 6% cellulose sulfate gel or a control gel intravaginally once or twice daily for 14 intramenstrual days, as follows:

Study Cohort	n CS gel	n Control gel	Frequency of Use
1: Sexually Abstinent	12	12	Once Daily
2: Sexually Abstinent	12	12	Twice Daily
3: Sexually Active and their male sexual partners	12 6	12 6	Once Daily
4: Sexually Active and their male sexual partners	12 10	12 10	Twice Daily

Study Duration: Accrual will require up to ++ 18 months. Each female participant will be followed for 14 days of product use and the entire study should be completed within ++3 19 months.

2. In the protocol Section 2.4.1:

This is a multisite, phase I, double blind, randomized, controlled frequency escalation study of 6% CS gel to be conducted among up to 96 80 sexually abstinent, and sexually active HIV-infected women from Birmingham, AL; New York, NY; Philadelphia, PA; and Providence, RI. Sexually active participants' male partners also will be included in the study.

Female study participants will complete once or twice daily intravaginal application of 6% CS gel or control gel for 14 consecutive days between menses. The control arms serve to provide information regarding signs, symptoms and/or morbidity that may be attributed to normal variation and/or the study procedures (e.g., speculum insertion) or use of applicator rather than the investigational product studied. The frequency of application will be escalated across "cohorts" of 24 study participants each 12 assigned at random to apply CS gel and 12 Cohorts 1 and 2 consisting of 24 women each, Cohort 3 consisting of 12 women, and Cohort 4 consisting of 20 women assigned at random to apply the control gel— as follows:

Study Cohort	n CS gel	n Control gel	Frequency of Use
1: Sexually Abstinent	12	12	Once Daily
2: Sexually Abstinent	12	12	Twice Daily
3: Sexually Active and their male sexual partners	12 6	12 6	Once Daily
4: Sexually Active and their male sexual partners	12 10	12 10	Twice Daily

Each study site will target enrollment of six-20 -participants.— three assigned to apply CS gel and three assigned to apply the control gel in each cohort.—Within Cohorts 1 and 2, accrual of six participants at each of the four study sites is targeted. Within Cohort 3, accrual of three participants at each of the four study sites, and within Cohort 4, accrual of 5 participants at each of the four study sites, and within Cohort 4, accrual of 5 participants at each of the four study sites is targeted. Ideally, at each site, three of the six participants enrolled in Cohorts 1 and 2, at most two of the three participants enrolled in Cohort 3, and at most three of the five participants enrolled in Cohort 4 will be assigned at random to apply CS gel at the assigned frequency (once or twice daily). The other women in each cohort will be assigned to apply the control gel. However, with prior approval of the Protocol Chair, enrollment "slots" may be shifted across sites in the event that a site encounters unexpected difficulty in meeting its accrual targets.

- 3. In the protocol Section 2.4.3, second bullet:
 - Within each cohort of 24 participants accrued across sites (24 each in Cohorts 1 and 2, 12 in Cohort 3 and 20 in Cohort 4), if two women experience a grade 3 AE judged possibly, probably, or definitely related to product use, accrual will be suspended at all sites and a safety data review will be undertaken to determine whether to continue the study, as described in Section 6.1. AEs will be defined as in Section 6 and graded according to the DAIDS Serious Adverse Experience (SAE) Reporting Manual for the HPTN and the DAIDS Toxicity Table.
- 4. In the protocol Section 3.0:

Up to 96 80 HIV-infected women will be included in this study, as will up to 48 32 HIV-infected male partners of sexually active female participants. Participants will be selected for the study according to the criteria in Section 3.1 and 3.2. They will be recruited as described in Sections 3.3 and 3.4 and assigned to a study product group as described in Section 7.4. Participant retention procedures are described in Section 3.6 and conditions for withdrawal from the study are described in Section 3.7.

5. In the protocol Section 3.4, third paragraph:

Women found to be presumptively eligible at the Screening Visit will be scheduled for an Enrollment Visit to take place 3-5 **2-6** days following **the end of** their next menstrual period, but within 42 days of the Screening Visit. (Women who are not enrolled within 42 days of screening must repeat all screening evaluations.) At this visit, female participants' eligibility will be confirmed according to the procedures described in Section 5.2; confirmed eligible participants will be randomized (see Section 7.4) and enrolled in the study.

6. In the protocol Section 7.3:

As noted in Section 2.4 up to 96 **80** female participants and up to 48 **32** male partners will be included in this study. Female participants will be enrolled into four cohorts, of 24 women each, Cohorts 1 and 2 consisting of 24 women each, Cohort 3 consisting of 12 women, and Cohort 4 consisting of 20 women. Within each cohort Cohorts 1 and 2, accrual of six participants at each of the four study sites is targeted, within Cohort 3, accrual of three participants at each of the four sites is targeted, and with Cohort 4, accrual of 5 participants at each of the four study sites is targeted. If for some reason a site experiences difficulty reaching its accrual targets, consideration will be given to shifting enrollment "slots" to the other sites, with prior approval of the Protocol Chair.

Ideally, at At each site, three of the six participants enrolled in each cohort, Cohorts 1 and 2, at most two of the three participants enrolled in Cohort 3, and at most three of the five participants enrolled in Cohort 4 will be assigned at random to apply CS gel at the assigned frequency (once or twice daily). The other three women in each cohort will be assigned to apply the control gel. Also at each site, accrual of each cohort will proceed sequentially, after the completion of follow-up of all participants in the prior cohorts, provided accrual is not suspended per the provisions of Section 2.4.3.

As a means to characterize the statistical properties of this study Cohorts 1 and 2, the following table presents the probability of observing zero, at least one, and two or more safety endpoints among groups of 12 women for various "true" event rates:

Event Rate	P (0 events n=12)	P (≥1 event n=12)	P (> 2 events n=12)
1%	0.89	0.11	0.01
5%	0.54	0.46	0.12
10%	0.28	0.72	0.34
15%	0.14	0.86	0.56
25%	0.03	0.97	0.84
35%	0.01	0.99	0.96
45%	< 0.01	>0.99	0.99

For example, if the true rate of a given endpoint in **Cohorts 1 or 2** is five percent, the probability that the endpoint will be observed in at least one of 12 women is 0.46. In addition, with a true rate of five percent, 12 women provide 88 percent power to exclude endpoint rates greater than 35 percent (i.e., the probability of observing 0 or 1 endpoint is less than 0.05 when the true rate is 35 percent, while this probability is 0.88 when the true rate is five percent).

The statistical properties of this study **Cohorts 1 and 2** also may be characterized by the width of confidence intervals (CI) around observed event rates. The following table presents the exact 95 percent CIs around endpoint rates when zero, one, or two endpoints are observed among 12 women:

No. Endpoints Observed	Lower Bound of CI	Upper Bound of CI
0	0.0%	26.5%
1	0.2%	38.5%
2	2.1%	48.4%

The properties described above are fairly robust relative to possible non-adherence to the study treatment regimen (as defined in Section 4.4). For example, if two women per cohort **in Cohorts 1 and 2** were non-adherent to the regimen, a subgroup analysis of the 10 adherent participants in the cohort would provide 74 percent power to exclude event rates greater than 45 percent for a given toxic event rate of 10 percent, and a pooled group of 20 participants would provide 74 percent power to exclude event for a given toxic event rate of five percent.

As a means to characterize the statistical properties of Cohort 3, the following table presents the probability of observing zero, at least one, and two or more safety endpoints among groups of 6 women for various "true" event rates:

Event Rate	P (0 events	P (> 1 event	P (> 2 events
Event Kate	n=6)	n=6)	n=6)
1%	0.94	0.06	<0.01
5%	0.74	0.26	0.03
10%	0.53	0.47	0.11
15%	0.38	0.62	0.22
25%	0.18	0.82	0.47
35%	0.08	0.92	0.68
45%	0.03	0.97	0.84

For example, if the true rate of a given endpoint in Cohort 3 is five percent, the probability that the endpoint will be observed in at least one of 6 women is 0.26. In addition, with a true rate of five percent, 6 women provide 97 percent power to exclude endpoint rates greater than 59 percent (i.e., the probability of observing 0 or 1 endpoint is less than 0.05 when the true rate is 59 percent, while this probability is 0.97 when the true rate is five percent).

The statistical properties of Cohort 3 also may be characterized by the width of confidence intervals (CI) around observed event rates. The following table presents the exact 95 percent CIs around endpoint rates when zero, one, or two endpoints are observed among 6 women:

No. Endpoints Observed	Lower Bound of CI	Upper Bound of CI
0	0.0%	45.9%
1	0.4%	64.1%
2	4.3%	77.7%

As a means to characterize the statistical properties of Cohort 4, the following table presents the probability of observing ze ro, at least one, and two or more safety endpoints among groups of 10 women for various "true" event rates:

Event Rate	P (0 events	P (> 1 event	P (> 2 events
Event Kate	n=10)	n=10)	n=10)
1%	0.90	0.10	<0.01
5%	0.60	0.40	0.09
10%	0.35	0.65	0.26
15%	0.20	0.80	0.46
25%	0.06	0.94	0.76
35%	0.01	0.99	0.91
45%	<0.01	>0.99	0.98

For example, if the true rate of a given endpoint in Cohort 4 is five percent, the probability that the endpoint will be observed in at least one of 10 women is 0.40. In addition, with a true rate of five percent, 10 women provide 91 percent power to exclude endpoint rates greater than 40 percent (i.e., the probability of observing 0 or 1 endpoint is less than 0.05 when the true rate is 40 percent, while this probability is 0.91 when the true rate is five percent).

The statistical properties of Cohort 4 also may be characterized by the width of confidence intervals (CI) around observed event rates. The following table presents the exact 95 percent CIs around endpoint rates when zero, one, or two endpoints are observed among 10 women:

No. Endpoints Observed	Lower Bound of	Upper Bound of
0	0.0%	30.9%
1	0.3%	44.5%
2	2.5%	55.6%

7. In the protocol Section 7.4:

Upon enrolling in the study, female participants will be assigned at random to apply either 6% CS gel or the control gel. Randomization will be stratified by cohort and by site to **help** ensure equal balanced assignment to each product within each cohort at each site. Specifically, provided each site meets its accrual target of six women per cohort, three women per cohort at each site will be assigned to apply CS gel, and three women per cohort at each site will be assigned to apply the control gel.

8. In the Cohort 1 and 2 Sample Informed Consent, Purpose of the study, last paragraph:

The study staff here are conducting this study with funding from the US National Institute of Allergy and Infectious Diseases (NIAID). The Contraceptive Research and Development Program (CONRAD) also is sponsoring this study. About 96 80 women and 48 32 men from Birmingham, AL; Providence, RI; Philadelphia; PA, and New York, NY will take part in the study. The study will last about 13-19 months. Your part will last about two months.

9. In the Cohort 3 and 4 Sample Informed Consent, Purpose of the study, last paragraph:

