The properties described above are fairly robust relative to possible nonadherence to the study treatment regimen (as defined in Section 4.4). For example, if two women per cohort were non-adherent to the regimen, a subgroup analysis of the 10 adherent participants in the cohort would provide 74 percent power to exclude event rates greater than 45 percent for a given toxic event rate of 10 percent, and a pooled group of 20 participants would provide 74 percent power to exclude event rates greater than 25 percent for a given toxic event rate of five percent.

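### Section 7.3's example does not support its claim that power in Cohorts 1 and 2 withstands non-adherence: like for like, 88% falls to 60%, and two women per cohort should read two per product arm

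*Protocol*

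**What the plan says.** For Cohorts 1 and 2 (24 women each, 12 per product), Section 7.3 states that "12 women provide 88 percent power to exclude endpoint rates greater than 35 percent". The assumption is "with a true rate of five percent", and the exclusion rule is given in brackets: "the probability of observing 0 or 1 endpoint is less than 0.05 when the true rate is 35 percent". Parallel sentences, added by the letter of 1 August 2003, cover Cohort 3 ("6 women provide 97 percent power to exclude endpoint rates greater than 59 percent") and Cohort 4 ("10 women provide 91 percent power to exclude endpoint rates greater than 40 percent").

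Precision is then described a second way, by "exact 95 percent CIs around endpoint rates when zero, one, or two endpoints are observed among 12 women", with matching tables for 6 and 10 women.

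Between the Cohort 1–2 figures and the Cohort 3 figures comes the claim at issue: "The properties described above are fairly robust relative to possible non-adherence to the study treatment regimen". Its illustration supposes two non-adherent women per cohort and says that "a subgroup analysis of the 10 adherent participants in the cohort would provide 74 percent power to exclude event rates greater than 45 percent", here at a true rate of 10%. It adds a pooled group of 20 with 74% power at a true rate of 5%. The excluded rate for that pooled example, 25%, is taken from Section 7.3 of the base protocol, because the words are absent from the amended sentence as it reads here.

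**The concern.** A robustness statement should hold everything fixed except the disturbance. Here the disturbance is the loss of two women from an arm of 12. The single-cohort example also raises the excluded rate by 10 percentage points and doubles the true rate. A reader who sets 74% beside 88% learns nothing about the effect of losing two women.

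The denominator is also wrong. A cohort has 24 women, so two non-adherent women leave 22 adherent participants in the cohort, not 10.

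At stake is a stated property of a small design. Someone planning an adherent-only look would believe that the ability to exclude 35% largely survives two non-adherent women per arm. Under the protocol's rule it does not.

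**Working it through.** **Inputs (Section 7.3).** n = 12 per arm, excluded rate 35%, true rate 5%. Non-adherence example: n = 10, 45%, 10%. Pooled example: n = 20, 25%, 5%. Rule: a count of at most k events excludes rate p0 if P(X ≤ k | n, p0) < 0.05. Power is P(X ≤ k | n, true rate) for the largest such k. I take the pooled 20 to be 24 women on one product across Cohorts 1 and 2, less two per arm: 24 − 2×2 = 20.

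**Formula.** P(X ≤ 1 | n, p) = (1−p)^n + n·p·(1−p)^(n−1).

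**Step 1: the stated figures reproduce.**
- n = 12: P(X ≤ 1 | 35%) = 0.0424 < 0.05. Power at 5% = 0.540 + 0.341 = 0.882 (88%).
- n = 6: P(X ≤ 1 | 59%) = 0.0458. Power at 5% = 0.967 (97%).
- n = 10: P(X ≤ 1 | 40%) = 0.0464. Power at 5% = 0.914 (91%).
- Non-adherence, n = 10: P(X ≤ 1 | 45%) = 0.0233. Power at 10% = 0.736 (74%).
- Pooled, n = 20: P(X ≤ 1 | 25%) = 0.0243. Power at 5% = 0.736 (74%).

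**Step 2: remove two women and change nothing else.** For 10 women at 35%, P(X ≤ 1) = 0.65^10 + 10×0.35×0.65^9 = 0.0135 + 0.0725 = 0.086, which fails the 0.05 rule. The protocol's own n = 10 table shows the same: P(≥2) = 0.91 at 35%, so P(0 or 1) is about 0.09. Only zero events qualifies, and power is 0.95^10 = 0.599.

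| Excluded / true rate | Full group | After loss |
|---|---|---|
| 35% / 5% | n = 12, ≤1 event (tail 0.042): 88% | n = 10, 0 events (tail 0.0135): 60% |
| 45% / 10% | n = 12, ≤2 events (tail 0.042): 89% | n = 10, ≤1 event (tail 0.023): 74% |
| 25% / 5%, pooled | n = 24, ≤2 events (tail 0.040): 88% | n = 20, ≤1 event (tail 0.024): 74% |

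**Step 3: take the protocol's move from 88% to 74% apart.** Start at n = 12, 35%, 5%: 88%. Drop to n = 10: 60%. Raise the excluded rate to 45%: one event now qualifies and power is 91%. Raise the true rate to 10%: 74%. The changes pull in opposite directions, and the drop caused by losing two women is hidden among them.

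**Step 4: the interval tables beside the power sentences.** For one event, the upper bounds are:

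| n | Rate said to be excluded | One-sided 95% | Two-sided 95% (printed) |
|---|---|---|---|
| 12 | 35% | 33.9% | 38.5% |
| 6 | 59% | 58.2% | 64.1% |
| 10 | 40% | 39.4% | 44.5% |

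The power sentences match the one-sided bounds and the printed tables are two-sided. Neither is labelled.

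**The case against.** Several counter-arguments have weight.

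- **Discreteness.** The fall from 88% to 60% is partly binomial discreteness: the permitted count drops from one event to none. If the excluded rate moves only from 35% to 40%, ten women have 91% power at a true rate of 5%, as the Cohort 4 sentence says. The printed two-sided bounds also widen only moderately from n = 12 to n = 10: 26.5% to 30.9%, 38.5% to 44.5% and 48.4% to 55.6% for zero, one and two events. This stands and belongs in the restated text.
- **The loss depends on the rule.** At 2.5% per tail, power does not fall: 54% to 60% (35%/5%), 66% to 74% (45%/10%), and 66% to 74% pooled (25%/5%). True, but Section 7.3 states the 5% rule, and the claim has to be judged by it.
- **The choice of 45% has an innocent explanation.** Allowing one event, 45% is the first row of the protocol's table that passes the 5% rule with 10 women. That explains the changed excluded rate. It does not explain the changed true rate, and it does not make the comparison like for like.
- **Practical weight.** Section 7.6 includes all randomized participants in all analyses and tabulates the primary endpoints. The adherent subgroup is an illustration and no decision depends on it. This stands and limits the severity.

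A reader might also infer that the two-sided tables contradict the power figures, so that the true powers are 54%, 74% and 60% instead of 88%, 97% and 91%. The protocol does not support that. Each power sentence prints its own rule, the one-sided bounds do lie below 35%, 59% and 40%, the tables are offered as a second description, and Section 7.6 plans no interval-based exclusion. Nor does the non-adherence paragraph switch to a 2.5% level: both of its examples also follow from the 5% rule, since two events would give 0.0996 (n = 10, 45%) and 0.091 (n = 20, 25%).

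**Conclusion.** The robustness claim for Cohorts 1 and 2 is not shown by its example and does not hold for the headline figure. Under the stated one-sided 5% rule, losing two women per arm cuts power to exclude 35% at a true rate of 5% from 88% to 60%, a loss of 28 percentage points. The losses are 15 points at 45%/10% (89% to 74%) and 14 points pooled (88% to 74%). These figures assume exact binomial counts, two non-adherent women in each arm, and a pooled group of 24 before the loss.

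The per-cohort count is a plain slip. Even if both non-adherent women fell in one arm, the cohort would still have 22 adherent participants; the figures of 10 and 20 both require two per arm.

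The unlabelled difference between one-sided power statements and two-sided tables is a matter of clarity. The 88%, 97% and 91% need no change, and the claim of robustness is not made for the Cohort 3 or Cohort 4 figures. Severity is minor.

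**What to change.** In Section 7.3 as amended:

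1. Replace the robustness sentence and its single-cohort example with like-for-like figures: with two non-adherent women per product arm, power falls from 88% to 60% (exclude 35%, true rate 5%) and from 89% to 74% (exclude 45%, true rate 10%); pooled over two cohorts, 24 to 20 women, from 88% to 74% (exclude 25%, true rate 5%). Add that 10 women have 91% power at a true rate of 5% if the excluded rate is 40% instead of 35%.
2. Change the non-adherence count from per cohort to per product arm, and refer to 10 adherent participants in the arm.
3. Label the power statements as one-sided 5% (one-sided 95% upper bounds) and the tables as two-sided 95%. Note that with one event the two-sided upper bounds of 38.5%, 64.1% and 44.5% lie above 35%, 59% and 40%.

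The cost is wording in one section and a less favourable statement about non-adherence. Sample size, analyses and the suspension rule are unaffected.
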